2.3.3 Safety measures

- Dose selection was based on a sound preclinical package including 4 week toxicological studies (see [Section 1.2.3](#)) and non-clinical pharmacology data ([Section 1.2.1](#)).

Careful selection of starting dose as described in [Section 2.1](#).

Dose escalation will be shallow with an increase of not more than 1.5 fold at the higher dose groups.

Proprietary confidential information © 2018 Boehringer Ingelheim International GmbH or one or more of its affiliated companies

- Measurement of BI 1323495 plasma concentrations and preliminary determination of PK parameters (C_{max} , AUC_{0-24} , see [Section 7.3.4](#)). For precautionary reasons, drug plasma concentrations in this healthy volunteer trial should not exceed a C_{max} of _____ or an AUC_{0-24} of _____ and will be considered as a preliminary threshold (see [Section 2.1](#)). Further dose progression would only be allowed after a safety interim analysis and filing and approval of a substantial CTP amendment.
- For safety reasons, each dose group of 8 subjects (6 on active, 2 on placebo) will be divided into three cohorts. In the 1st cohort only 2 subjects will be treated: one subject will receive active treatment, the other subject will receive placebo. If BI 1323495 treatment is safe and well tolerated in this first cohort, the following 2 subjects on active will be treated in the 2nd cohort with drug administration occurring not earlier than 24 hours after the first subject of the dose level received active treatment. The remaining 4 subjects (either active or placebo) are the third cohort and will be treated no sooner than 48 hours following the 1st cohort. Within each cohort, a time interval of at least 10 min will be maintained between administrations of study drug.

This design ensures that between first and second active dose of each dose level there is a time interval of at least 24 hours, which is expected to be sufficient to detect relevant first acute effects of BI 1323495.

- Only if the respective dose of BI 1323495 was safe and showed acceptable tolerability and if no stopping criterion was met (see [Section 3.3.4.2](#)), the next higher dose will be given at least 6 days later (referring to the 1st subject of each dose group). A documented Safety Review must take place prior to each dose escalation (see [Section 3.1](#)).
- An extensive safety laboratory will be performed (see [Section 5.2.3](#)).

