3. DESCRIPTION OF DESIGN AND TRIAL POPULATION

3.1 OVERALL TRIAL DESIGN AND PLAN

This single-rising dose trial is designed as single-blind, partially randomised, and placebo-controlled within parallel dose groups.

A total of 64 healthy male subjects is planned to participate in the trial, according to 8 sequential groups comprising 8 subjects per group. However, additional subjects may be entered to allow testing of additional doses on the basis of experience gained during the trial conduct (e.g., preliminary PK data), provided the planned and approved highest dose will not be exceeded. Thus, the actual number of subjects entered may exceed 64, but will not exceed 80 subjects entered. Such changes may be implemented via non-substantial CTP Amendments provided additional doses are used for the further evaluation of pharmacokinetics or pharmacodynamics in the absence of new safety signals. The addition of dose groups to further evaluate safety findings may be implemented only after notification of a substantial amendment.

Within each dose group, 6 subjects will receive the active drug and 2 will receive placebo. Only one dose is tested within each dose group. Each dose group will consist of 3 cohorts which will be treated subsequently for safety reasons.

The dose groups to be evaluated are outlined in Table 3.1: 1 below.

Table 3.1: 1 Dose groups

The dose groups will be investigated consecutively in ascending order of doses, maintaining a time interval of at least 6 days between the first drug administration in the previous dose group and the first drug administration of the subsequent dose group. The decision to proceed to the next dose group will be based upon the safety, tolerability, and pharmacokinetic data of the preceding dose groups. The next dose will only be given if, in the opinion of the investigator, no safety concerns arose in the preceding dose group (i.e., no dose-limiting events occurred) and if none of the pre-specified trial-specific stopping criteria were met (refer to [Section 3.3.4.2](#)).

A documented Safety Review must take place prior to each dose escalation. Furthermore, an unscheduled safety review meeting can be requested any time for any reasonable cause by the Principal Investigator (or an authorised deputy) or the sponsor of the study, e.g. because of any unforeseen adverse events, etc. Dose escalation will only be permitted if no safety

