Proprietary confidential information © 2018 Boehringer Ingelheim International GmbH or one or more of its affiliated companies

concerns exist in the opinion of the Principal Investigator (or an authorised deputy) and the trial clinical monitor (or an authorised deputy).

Although no formal Safety Review meeting will take place within a given dose group, safety will be continuously monitored during this trial, and an individual will only be dosed in the absence of any safety concern (i.e., no dose-limiting events occurred) and if none of the pre-specified trial-specific stopping criteria have been met (refer to [Section 3.3.4.2](#)).

The minimum data set for review consists of the following data:

- AEs in the current* and preceding dose groups including clinically relevant findings from ancillary safety testing listed below up to at least 48 h post-dosing.
Note: AEs may be ongoing at the time of Safety Reviews and AE information may be subject to change prior to Database Lock.
- Vital signs in the current* and preceding dose groups up to at least 48 h post-dosing
- Clinical laboratory tests in the current* and preceding dose groups up to at least 24 hours post-dose
- Preliminary PK data for selected time points as per [Section 7.3.4](#)
- Check of criteria for stopping subject treatment as per [Section 3.3.4.1](#)

**"Current dose group" means: all subjects of that dose group with at least 4 subjects being on active treatment.

The decision to escalate the dose will be made jointly by the Principal Investigator (or an authorised deputy) and the trial clinical monitor (or an authorised deputy) after in-depth analysis of all available safety data, especially SAEs (if occurred), AEs, and out-of-range laboratory results (if considered clinically significant). Safety Reviews can be conducted face-to-face or by video/telephone conference. The trial clinical monitor is responsible for organization and minutes of the reviews. Minutes will be signed off by the Principal Investigator (or an authorised deputy) and filed in the ISF and TMF.

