The investigator is allowed to alter the scheduled dose levels (e.g. add low and/or intermediate dose levels) on the basis of experience gained during the study, provided the planned and approved highest dose is not exceeded. In this case, the total number of subjects in this trial might increase. The investigator and/or the sponsor should stop dose escalation in case the safety evaluation leads to concerns that would not allow higher dosing.

An overview of all relevant trial activities is provided in the [Flow Chart](#). For visit schedules and details of trial procedures at selected visits, refer to [Sections 6.1](#) and [6.2](#), respectively.

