3.3.4.2 Discontinuation of the trial by the sponsor

Boehringer Ingelheim reserves the right to discontinue the trial overall or at a particular trial site at any time for any of the following reasons:

1. New toxicological findings or serious adverse events invalidate the earlier positive benefit-risk-assessment. Dose escalation will be terminated if more than 50% of the subjects at one dose level show drug-related and clinically relevant adverse events of moderate or severe intensity.

Proprietary confidential information © 2018 Boehringer Ingelheim International GmbH or one or more of its affiliated companies

No further subjects will be dosed without thorough re-evaluation of the benefit-risk ratio, if severe non-serious adverse events considered as drug-related by the investigator are reported in 2 subjects of the same dose group or if at least one drug-related serious adverse event is reported.

2. The expected enrolment goals overall are not met
3. Violation of GCP, or the CTP by a trial site or investigator, disturbing the appropriate conduct of the trial
4. The sponsor decides to discontinue the further development of the investigational product.
5. Dose escalation will be stopped as soon as at least 2 subjects at one dose level on active drug showed relevant individual QT prolongation, i.e. absolute QT or QTc greater than 500 which has been confirmed by a repeat ECG recording or QTc increase of greater 60 ms from baseline in connection with absolute QT or QTc greater than 500 ms, which has been confirmed by a repeat ECG recording.
6. Dose escalation will be stopped if the C_{max} or AUC_{0-24} of at least 1 subject of one dose group increases above the following exposure thresholds or if the estimated systemic exposure (group gMean values) of the next dose level is expected to exceed a C_{max} of nM or an AUC_{0-24} of nM*h. In this case, one or two dose levels lower than the planned next dose level may be given, as long as the expected systemic exposure (group gMean values) of each dose is not expected to exceed the aforementioned thresholds.

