7.6 DETERMINATION OF SAMPLE SIZE

It is planned to include a total of 64 subjects in this trial. The planned sample size is not based on a power calculation. The size of 8 subjects per dose group (6 on active treatment, and 2 on placebo) is commonly used in single-rising dose studies of the present type and is in general considered as sufficient for the exploratory evaluation of single dose safety and pharmacokinetics ([R95-0013](#)).

Additional subjects may be entered to allow testing of additional doses on the basis of experience gained during the trial conduct (e.g. preliminary PK data), provided the planned and approved highest dose will not be exceeded and none of the stopping criteria apply. Thus, the actual number of subjects entered may exceed 64, but will not exceed 80 subjects entered.

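### Criterion 6 does not say which trigger its lower-dose allowance follows, so a dose above the one where a subject exceeded the exposure limit could be given on expected gMean alone

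*Protocol*

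**What the plan says.** Criterion 6 in Protocol 3.3.4.2 opens: "Dose escalation will be stopped if the C_{max} or AUC_{0-24} of at least 1 subject of one dose group" rises above the exposure thresholds. The same sentence adds a second trigger, joined by an *or*: the predicted group gMean of the next level is above the thresholds. The next sentence begins: "In this case, one or two dose levels lower than the planned next dose level may be given". Its one condition is that the expected group gMean of each such dose stays within the thresholds.

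Other sections bear on the same situation:

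- **2.3.3**, directly after naming the Cmax and AUC0-24 threshold: "Further dose progression would only be allowed after a safety interim analysis and filing and approval of a substantial CTP amendment".
- **2.3.3**, on the next higher dose: "Only if the respective dose of BI 1323495 was safe and showed acceptable tolerability and if no stopping criterion was met", with a reference to 3.3.4.2.
- **3.1** sets a similar condition for the next dose group ("and if none of the pre-specified trial-specific stopping criteria were met") and for dosing any individual ("and if none of the pre-specified trial-specific stopping criteria have been met"), both times referring to 3.3.4.2.
- **3.1**, on changing the dose levels: "The investigator is allowed to alter the scheduled dose levels (e.g. add low and/or intermediate dose levels", as long as the highest approved dose is not exceeded. Added doses need an amendment, which is non-substantial only for PK or PD evaluation without new safety signals.
- **2.1.2** allows the maximum dose only if neither individual values at a lower dose nor predicted means exceed the limits. Otherwise escalation stops lower down.
- **7.6** allows additional subjects for additional doses "provided the planned and approved highest dose will not be exceeded and none of the stopping criteria apply".

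The threshold values are blacked out. The SAP does not deal with escalation.

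**The concern.** The two triggers carry different information. A predicted gMean above the threshold is a forecast about a dose nobody has received, and a smaller step is a sensible answer to it. An individual exceedance has already happened at the current dose. Criterion 6 gives both the same follow-up, and nothing in it keeps the follow-up dose at or below the one where the subject exceeded.

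This is a first-in-human trial in healthy men. After one of them exceeds the limit, criterion 6 can be read as allowing a higher intermediate dose, while 2.3.3 can be read as requiring a halt until an amendment is approved. The gMean condition does not replace the individual limit: a group gMean within the limit does not show that individuals at a higher dose will stay within it.

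**Working it through.** The plan gives no figure to reproduce. The check compares the texts and then illustrates how the situation could arise.

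**1. What each text says after one subject exceeds a threshold**

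| Section | A dose above that subject's dose |
|---|---|
| 3.3.4.2, criterion 6, first sentence | Escalation stops |
| 3.3.4.2, criterion 6, second sentence | Permitted if below the planned next level and expected gMean is within the thresholds |
| 2.3.3, amendment sentence | Only after a safety interim analysis and an approved substantial amendment |
| 2.3.3, next higher dose | Only if no stopping criterion was met |
| 2.1.2 (maximum dose) | Not given; escalation stops at lower doses |

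**2. Is such a dose feasible?** Protocol 4.1.1 gives DG 5 as 4 tablets and DG 6 as 6 tablets of one strength. Five tablets is therefore a possible intermediate level, 5/4 = 1.25 times DG 5. The cap of 80 subjects leaves room for (80 − 64)/8 = 2 extra groups, which fits one or two inserted levels.

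**3. When does the gMean condition let it through?** Assume dose proportionality and the same limit L for individuals and for gMean. The 5-tablet dose passes if 1.25 × gMean(DG 5) ≤ L, that is gMean(DG 5) ≤ L/1.25 = 0.80 L. The number of subjects who exceeded does not enter.

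**4. How often could both happen at DG 5?** The documents give no CV and no ratio of gMean to limit, so both are assumed. The model is one log-normal PK parameter with s = √ln(1 + CV²), simulated 400,000 times. The event is that the largest of n active values exceeds L while the sample gMean × 1.25 ≤ L. For n = 6:

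| CV | True gMean 40% of L | 50% | 60% | 70% | 75% |
|---|---|---|---|---|---|
| 20% | 0.000 | 0.001 | 0.029 | 0.163 | 0.209 |
| 30% | 0.005 | 0.053 | 0.214 | 0.386 | 0.377 |
| 50% | 0.147 | 0.350 | 0.527 | 0.540 | 0.481 |

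Section 3.1 accepts a Safety Review with 4 active subjects, and 7.3.4 accepts preliminary PK from 2. Over the same ratios, the ranges for CV 20%, 30% and 50% are 0–11%, 0.4–23% and 10–36% with 4, and 0–2%, 0.2–5% and 4–11% with 2.

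**5. What would the higher dose mean for the new subjects?** Take CV 30%, so s = √ln 1.09 = 0.294.

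- Current dose, gMean 70% of L: P(one subject > L) = 1 − Φ(ln(1/0.70)/0.294) = 0.112. P(at least 1 of 6) = 1 − 0.888⁶ = 0.51.
- After a 1.25-fold step, gMean 87.5% of L: P(one subject > L) = 0.325. P(at least 1 of 6) = 1 − 0.675⁶ = 0.91. The gMean condition is still met.
- If the gMean equals L, which criterion 6 also allows, half of the active subjects are expected above it and P(at least 1 of 6) = 1 − 0.5⁶ = 0.984, whatever the CV.

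**6. Does 7.6 matter?** Two inserted levels after a trigger in DG k give 8k + 16 subjects: 64 for k = 6 and 72 for k = 7. Without earlier added groups, the condition in 7.6 matters only when the total passes 64.

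**The case against.** The best defence is that criterion 6 already has a coherent reading. It opens by stopping escalation. The allowance is singular, is measured from the planned next level, and repeats the gMean language of the trigger just before it. So a forecast overshoot would permit a smaller step, and an individual exceedance would simply stop escalation. Section 2.1.2 points the same way. This reading is plausible and may be what the sponsor meant, but the wording does not require it.

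The lower levels could also be read as the current dose or below. Again nothing says so; an expected exposure for each dose suits untested levels, and 3.1 foresees intermediate ones.

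The amendment sentence in 2.3.3 might cover only progression beyond the threshold. It names no trigger, so this cannot be settled from the text.

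A reader might go further and infer three things that the documents do not support:

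- *That the Safety Review team has no rule.* Sections 2.1.2 and 2.3.3 point to stopping, and 3.1 requires an amendment for added doses and a joint decision by the Principal Investigator and the trial clinical monitor.
- *That 3.1 forbids whatever criterion 6 permits.* Section 3.1 refers to 3.3.4.2 for the criteria, and such a reference can bring in criterion 6 together with its own allowance. The 2.3.3 clause on the next higher dose refers there too, so the amendment sentence is the firmer ground.
- *That the subject who exceeded would be taken further above the limit.* Each subject receives one dose; any added exposure falls on new volunteers.

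The stated margins also stand. At the exposure limit, 2.1.2 gives NOAEL factors of 16 and 10 in one 4-week study and about 28 and 34 in another. At 1.25 times the limit, the smallest would be 10/1.25 = 8. The probabilities in the working show how often the ambiguity could arise; they do not measure harm.

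**Conclusion.** The point holds as an inconsistency in a stopping rule. Criterion 6 can be followed as written to a dose above the one where a subject exceeded the limit, with expected group gMean as the only exposure condition. The Safety Review, the amendment route in 3.1 and the other stopping criteria still apply. This does not fit the amendment requirement in 2.3.3 or, on its face, that section's condition for the next higher dose. It also goes against the intent of 2.1.2.

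The textual finding needs no numerical assumption. Its size does: between-subject CV, ratio of gMean to limit, dose proportionality, and equal individual and gMean limits are all assumed. Across the values shown for 6 active subjects, the result runs from 0% to 54%, so no single figure should be cited. The text should be corrected because a stopping rule in a first-in-human trial needs one reading.

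**What to change.** Replace the last sentence of criterion 6 with wording such as:

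*If the only trigger is the predicted group gMean of the next level, one or two levels below it may be given instead, provided the expected group gMean of each stays within the thresholds. If at least 1 subject exceeded a threshold, no dose above that subject's dose is given until a safety interim analysis has been done and a substantial amendment approved (Section 2.3.3).*

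Then align the other sections:

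- In 3.1 (both places) and in the 2.3.3 condition for the next higher dose, add: *except as allowed in Section 3.3.4.2, criterion 6*.
- In the 2.3.3 amendment sentence, state that it applies if any subject exceeds the threshold or if a dose expected to exceed it is proposed. Limiting it to individual exceedance would drop the requirement for doses predicted to pass the threshold.
- Matching edits in 7.6 and the synopsis are optional.

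The cost is one replaced sentence and a few short insertions, with no extra data and no change in planned sample size. The downside is that a higher dose after an individual exceedance waits for a substantial amendment, as 2.3.3 already says.

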3.3.5 Replacement of subjects

In case some subjects do not complete the trial or there is not a sufficient number of subjects on active within one dose group (see [Section 3.1](#)), the trial clinical monitor together with the trial pharmacokineticist and the trial statistician are to decide if and how many subjects will be replaced. A replacement subject will be assigned a unique study subject number, and will be assigned to the same treatment as the subject he replaces.

4. TREATMENTS

4.1 TREATMENTS TO BE ADMINISTERED

The investigational products have been manufactured by BI Pharma GmbH & Co. KG.

4.1.1 Identity of BI investigational and comparator products

The characteristics of the test products are given below:

Tablet

Substance: BI 1323495
Pharmaceutical formulation: Film-coated tablet
Source: BI Pharma GmbH & Co. KG, Germany
Unit strength:
Posology: 1-0-0 (DG 1), 3-0-0 (DG 2), 6-0-0 (DG 3)
Route of administration: p.o.
Duration of use: Single dose

Tablet

Substance: BI 1323495
Pharmaceutical formulation: Film-coated tablet
Source: BI Pharma GmbH & Co. KG, Germany
Unit strength:
Posology: 2-0-0 (DG 4), 4-0-0 (DG 5), 6-0-0 (DG 6)
Route of administration: p.o.
Duration of use: Single dose

Tablet

Substance: BI 1323495
Pharmaceutical formulation: Film-coated tablet
Source: BI Pharma GmbH & Co. KG, Germany
Unit strength:
Posology: 3-0-0 (DG 7), 4-0-0 (DG 8)
Route of administration: p.o.
Duration of use: Single dose

Proprietary confidential information © 2018 Boehringer Ingelheim International GmbH or one or more of its affiliated companies

The randomisation list with study subject numbers and allocated treatments will be provided to the trial site in advance. The allocation of subjects to study subject numbers will be performed prior to the first administration of trial medication. For this purpose, the subjects will be allocated to a study subject number by drawing lots. Once a subject number has been assigned, it cannot be reassigned to any other subject.

The randomisation procedure is described in [Section 7.5](#).

4.1.3 Selection of doses in the trial

The doses selected for this trial cover the sub-therapeutic as well as the estimated therapeutic range and include a safety margin (see [Section 1.2](#) and [2.1](#)).

4.1.4 Drug assignment and administration of doses for each subject

The treatments to be evaluated are outlined in [Table 4.1.4: 1](#) below. The number of units for placebo corresponds to the number of units of the respective dose level.

Table 4.1.4: 1 BI 1323495 and placebo treatments, oral administration

Dose	Substance	Pharmaceutical form	Unit strength	Number of units per administration	Total dose
1	BI 1323495	Film-coated tablet		1 tablet as single dose	
2	BI 1323495	Film-coated tablet		3 tablets as single dose	
3	BI 1323495	Film-coated tablet		6 tablets as single dose	
4	BI 1323495	Film-coated tablet		2 tablets as single dose	
5	BI 1323495	Film-coated tablet		4 tablets as single dose	
6	BI 1323495	Film-coated tablet		6 tablets as single dose	
7	BI 1323495	Film-coated tablet		3 tablets as single dose	
8	BI 1323495	Film-coated tablet		4 tablets as single dose	
1-8	Placebo*	Film-coated tablet	--	identical to respective active treatment	--

* Subjects receiving placebo are equally distributed across dose groups

The trial medication will be administered to the subjects, while in a standing or sitting position, as an oral dose together with about 240 mL of water under supervision of the investigating physician or an authorised designee. The so-called four-eye principle (two-person rule) should be applied for administration of trial medication and – if applicable – its preparation (e.g. reconstitution), if correct dosage cannot be ensured otherwise.

Proprietary confidential information © 2018 Boehringer Ingelheim International GmbH or one or more of its affiliated companies

Administration will be performed following an overnight fast, which is to start no later than 10 h before the scheduled dosing.

Subjects will be kept under close medical surveillance until 24 h following drug administration. During the first 4 h after drug administration, they are not allowed to lie down (i.e. no declination of the upper body of more than 45 degrees from upright posture except for medical examination), or to sleep. For restrictions with regard to diet see [Section 4.2.2.2](#).

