- A thorough ECG monitoring including continuous ECG measurement over 4 hours post-dose and repeated 12-lead ECGs during the observation period following drug administration. Dose escalation would be stopped as soon as at least 2 subjects at one dose level showed relevant QT prolongation (see [Section 3.3.4.2](#) for details).
- The subjects will stay at the trial site (BI Human Pharmacology Centre) for at least 34 hours after study drug administration. Based on an anticipated half-life of BI 1323495 of approximately _____ this is expected to cover the period of highest risk / peak effect.
- During in-house confinement the subjects will be under medical observation and thoroughly monitored for both expected and unexpected adverse events.

In summary, although not tested in humans to date, BI 1323495 has the potential to become an oral treatment for patients with _____. Based upon preclinical data for BI 1323495 and clinical information from competitor compounds as well as the implemented safety measures described above, healthy subjects will not be exposed to undue risks in relation to the important information expected from this trial as a basis for further clinical development of this compound. Healthy volunteers are not expected to have any direct benefit from participation in this first-in-man clinical trial with BI 1323495. Considering the medical need of the development of an effective treatment for patients with _____ the Sponsor considers

Proprietary confidential information © 2018 Boehringer Ingelheim International GmbH or one or more of its affiliated companies

that the benefit outweighs the potential risks and justifies exposure of healthy human volunteers.

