6.2.2 Treatment period

Each subject will receive one dose of the respective trial medication (BI 1323495 or placebo) at Visit 2.

Proprietary confidential information © 2018 Boehringer Ingelheim International GmbH or one or more of its affiliated companies

Trial medication will be taken orally by each subject under direct supervision of the investigator or designee. Details on treatments and procedures of administration are described in [Section 4.1.4](#).

Study participants will be admitted to the trial site in the morning of Day 1 and kept under close medical surveillance for at least 34 h following drug administration. The subjects will then be allowed to leave the trial site after formal assessment and confirmation of their fitness by the investigator or designee. From Day 3 onwards, the study will be performed in an ambulatory fashion.

For details on time points and procedures for collection of blood samples for PK analysis, refer to [Flow Chart](#) and [Section 5.5.2](#).

For details on time points and procedures for collection of blood samples for PD analysis, refer to [Flow Chart](#) and [Section 5.6.2](#).

The safety measurements performed during the treatment period are specified in [Section 5.2](#) of this protocol and in the Flow Chart. For details on time points for all other trial procedures, refer to the Flow Chart. AEs and concomitant therapy will be assessed continuously from screening until the end of trial examination.

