11. DESCRIPTION OF GLOBAL AMENDMENT(S)

Number of global amendment	1	
Date of CTP revision	4 July 2018	
EudraCT number	2017-004899-62	
BI Trial number	1405-0001	
BI Investigational Product(s)	BI 1323495	
Title of protocol	Safety, tolerability, pharmacokinetics, and pharmacodynamics of single rising oral doses of BI 1323495 in healthy male subjects (single-blind, partially randomised, placebo-controlled parallel group design)	
To be implemented only after approval of the IRB / IEC / Competent Authorities		
To be implemented immediately in order to eliminate hazard – IRB / IEC / Competent Authority to be notified of change with request for approval		
Can be implemented without IRB / IEC / Competent Authority approval as changes involve logistical or administrative aspects only		
Section to be changed	
1) Synopsis2) Flow Chart3) 2.1 Rationale for performing the trial4) 2.1.2 Maximum dose and dose escalation5) 2.3.3 Safety measures6) 3.1 Overall trial design and plan7) 3.3.3 Exclusion criteria8) 3.3.4.2 Discontinuation of the trial by the sponsor9) 5.2.3 Assessment of safety laboratory parameters10) 5.6.1 Biochemical and cellular biomarkers11) 6.2.2 Treatment period12) 7.3.4 Preliminary PK analyses13) 7.3.6 Determination of sample size	

Proprietary confidential information © 2018 Boehringer Ingelheim International GmbH or one or more of its affiliated companies

Number of global amendment	1
Description of change	
1)+ 6)+ 13) 2)
 
3) "X" deleted in heading 4) Individual exposure limits defined 5) Individual exposure limits defined; inhouse observation period extended 7) Amended eGFR value (exclusion criterion 25) and limits for liver enzyme values (new exclusion criterion 27) 8) Stopping criteria with respect to adverse events and exposure limits revised 9) Added parameter Set D in Table 5.2.3: 1 and specified that fasting is not required for timepoints when Set D is to be taken 10) 11) Text adapted to extended inhouse observation period 12) Specified methods and software used for preliminary PK analyses

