## 6.2        **IMPORTANT PROTOCOL DEVIATIONS**

Data discrepancies and deviations from the CTP will be identified for all treated subjects.

Consistency check listings (for identification of deviations of time windows) and a list of protocol deviations (e.g. deviations in drug administration, in blood sampling times, etc.) will be provided to be discussed at the Report Planning Meeting and database lock meeting (RPM/DBLM). At this meeting, all manual deviations identified at the sites by the CRAs and deviations too complex to program will be reviewed by the trial team to decide which are considered important. For definition of important protocol deviations (iPD), and for the process of identification of these, refer to the Boehringer Ingelheim (BI) SOP "Identify and Manage Important Protocol Deviations (iPD)" ([2](#)).

If any iPDS are identified, they are to be summarised into categories and will be captured in the RPM/DBLM minutes via an accompanying Excel spreadsheet (3). The following table contains the categories which are considered to be iPDS in this trial. If the data show other iPDS, this table will be supplemented accordingly by the time of the RPM/DBLM at the latest.

Important protocol deviations will be summarised and listed.

Table 6.2: 1 Important protocol deviations

Category/Code		Description
A		Entrance criteria not met
	A1	Inclusion criteria violated
	A2	Exclusion criteria violated
B		Informed consent
	B1	Informed consent not available
	B2	Informed consent too late
C		Trial medication and randomisation
	C1	Incorrect trial medication taken
	C2	Randomisation not followed
	C3	Non-compliance
	C4	Incorrect intake of trial medication
D		Concomitant medication
	D1	Concomitant medication with the potential to affect the assessment of the trial medication
E		Missing data *
	E1	None
F		Incorrect timing
	F1	Certain deviations from time schedule used to measure secondary data
G		Other trial specific important deviations
	G1	Incorrect intake of meal before administration of treatment
	G2	Protocol deviations affecting safety and rights

 Time deviations will only be flagged as iPDS, when leading to exclusion of the entire subject from an analysis set

\* Missing visits, evaluations, and tests will be considered missing data, not protocol deviations

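### Protocol 4.1.4 ends close medical surveillance at 24 h after dosing, but Protocol 6.2.2 requires it for at least 34 h

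*Protocol*

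**What the plan says.** Three places in the current protocol deal with how long subjects are watched after the single dose.

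- **Section 4.1.4**, after the fasting instruction and before the posture rule: "Subjects will be kept under close medical surveillance until 24 h following drug administration".
- **Section 6.2.2**, on the treatment period: subjects are admitted on the morning of Day 1 and "kept under close medical surveillance for at least 34 h following drug administration". Discharge comes only after that: "The subjects will then be allowed to leave the trial site after formal assessment and confirmation of their fitness by the investigator or designee".
- **Section 2.3.3**, among the safety measures: "The subjects will stay at the trial site (BI Human Pharmacology Centre) for at least 34 hours after study drug administration". It adds: "During in-house confinement the subjects will be under medical observation and thoroughly monitored for both expected and unexpected adverse events". The sponsor explains the length of stay by the anticipated half-life and expects it to span the time of greatest risk.

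In the SAP, Section 6.2 says "Data discrepancies and deviations from the CTP will be identified for all treated subjects", and category G2 of its Table 6.2: 1 is "Protocol deviations affecting safety and rights".

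**The concern.** Sections 4.1.4 and 6.2.2 apply one term, close medical surveillance, to the same people and count from the same time, but give different durations. A site that steps surveillance down at 24 h follows 4.1.4 and breaches 6.2.2.

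What is at stake is the clarity of a safety rule in a compound's first human trial. The disputed hours fall inside the stay that Section 2.3.3 justifies as covering the period of highest risk. A secondary consequence is that the deviation review in SAP 6.2 would have no single standard if it had to judge a reduction in surveillance at 24 h, because the answer depends on the section consulted.

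Estimation is not at stake. Protocol 5.2.2.2, 6.2.2 and 7.3.3 collect adverse events to the end of trial and count them as on treatment up to that point, whatever the surveillance level on Day 2.

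**Working it through.** There is no power or error-rate figure to reproduce: Protocol 7.6 states that the sample size has no power basis, and the point rests on stated times alone. The check sets the sections side by side.

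| Item | Section | Stated time after dosing |
|---|---|---|
| Close medical surveillance | Protocol 4.1.4 | ends at 24 h |
| Close medical surveillance | Protocol 6.2.2 | at least 34 h |
| Stay at the trial site | Protocol 2.3.3 | at least 34 h |
| Earliest departure | Protocol 6.2.2 | after the 34 h minimum and a fitness assessment |

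**Step 1: surveillance level.** Conflict = minimum in 6.2.2 − end point in 4.1.4 = 34 h − 24 h = 10 h. Because 34 h is a minimum, the conflict is at least 10 h.

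**Step 2: length of stay.** Conflict = 34 h (2.3.3) − 34 h (6.2.2) = 0 h. These two sections agree on the stay, and nothing in 4.1.4 allows a subject to leave at 24 h.

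**Step 3: can both sentences stand?** They could if the protocol defined a higher level of surveillance to 24 h and a lower one afterwards. No visible section does so, and 6.2.2 applies the same term as 4.1.4 through to 34 h. Section 2.3.3 speaks of observation and monitoring during confinement. It neither uses nor defines the disputed term, so it cannot settle which time governs. No order of precedence between sections is stated.

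**Step 4: who is affected.** Both sentences cover every treated subject without distinction of dose group or treatment: 64 planned, at most 80 (Protocol 7.6).

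**Context only.** The entry for global amendment 1 in Protocol Section 11 records a longer in-house observation period, with the note "Text adapted to extended inhouse observation period" for Section 6.2.2. It lists 2.3.3 and 6.2.2 among the changed sections, but not 4.1.4. This suggests that 4.1.4 was not updated at that time, but does not prove it. The finding does not rest on it, since it compares current text with current text.

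**The case against.** The best case for leaving the text alone has four parts.

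1. **The longer rule satisfies both sentences.** Section 4.1.4 does not expressly permit a reduction at 24 h, so a site that keeps close surveillance for 34 h breaches nothing. This is true of a cautious site. But an instruction to do something until 24 h is naturally read as ending there, and 4.1.4 read alone requires nothing more afterwards.

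2. **The window is already covered.** Section 2.3.3 requires medical observation for the whole confinement, and the documents never define that as a lower level than close surveillance. This stands as a limit on the consequence: no subject is unobserved between 24 h and 34 h. It does not tell the reader which of two stated durations applies.

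3. **The sections have different roles.** Section 6.2.2 sets admission, stay and discharge, and refers to 4.1.4 only for treatments and administration. A reader looking for the observation period would probably go to 6.2.2 and 2.3.3, which agree. This weakens the ambiguity without removing it.

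4. **The deviation argument is thin.** Category G2 is general, importance is decided by the trial team at the report planning and database lock meeting, and nothing shows that surveillance intensity is recorded as a separate item. This is fair. The SAP point is supporting only, and the finding stands without it.

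It is also true that nothing downstream moves. The minimum data set for dose escalation in Protocol 3.1 (adverse events and vital signs to at least 48 h, laboratory tests to at least 24 h) does not depend on this sentence.

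**Conclusion.** The concern holds. Two complete, current sections give the same surveillance requirement different durations, which leaves at least 10 h after dosing (24 h to 34 h) with contradictory instructions for every treated subject. The stay itself is consistent, with 0 h in dispute. There is no consequence for the primary endpoint, the sample size or the analysis. The practical effect is at the minor end, but the text is wrong as written and should be corrected because it is a safety rule in a first-in-human trial.

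The conclusion assumes that close medical surveillance means the same thing in both sections, as the shared wording implies. The Flow Chart is not visible in the public text, so whether scheduled assessments change at 24 h could not be checked. Even if it gives a time, the two sections would still disagree. No view is taken on which duration is right.

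**What to change.** Reconcile Sections 4.1.4 and 6.2.2 so that one duration of close medical surveillance applies to all subjects, and check the result against Section 2.3.3 and the Flow Chart. If two levels are intended, name each, say what it involves and give the time at which one passes to the other. Alternatively, remove the duration from 4.1.4 and refer to the section that governs, once the sponsor has confirmed the intended time.

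The cost is a wording change at the next amendment. Sample size, endpoints and analysis stay as they are.
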